## 1.0 BACKGROUND/ RATIONALE (REQUIRED)

**Prostate (PC), breast (BC), and colorectal (CRC) cancer survivors account for 51% of the 15.5 million cancer survivors in the U.S.[1] – a figure expected to grow by 10 million in less than a decade.** Nearly all of these cancer survivors are over age 40 and are expected to live many years, if not decades, after their cancer diagnosis, raising concerns about the impact of cancer on their long-term health, work ability and health care expenses. Compared to the general population, cancer survivors have a higher risk of recurrence than their initial risk for cancer, dying of CVD than cancer [2, 3], and reporting functional limitations and/or an inability to work [4-8]. Cancer survivors are more likely to have multiple chronic conditions besides cancer that are associated with up to \$13K in medical expenditures and \$9K in lost productivity per survivor, per year [9]. Most cancer survivors are married when diagnosed and cancer will also threaten the physical and mental health of their aging spouse and the quality of their marital relationship - *in effect doubling the societal and economic impact of cancer*. Spouse caregivers experience significant health declines, such as increased CVD risk [10, 11], and are at greater risk for mobility limitations [12] and mortality than other family caregivers [13-19].

**Since husbands and wives typically share environments, behaviors and values the health and wellbeing of couples becomes closely intertwined, where the physical and mental health of one partner influences the others' [20-22].** Thus, focusing solely on the survivor or spouse may miss a critical component of the cancer experience – i.e., the interdependent nature of the couple. Declining physical health of a spouse can also profoundly impact on marital quality [22-25] and chronic illness can rob a couple of intimacy, further straining the relationship. Recent evidence suggests that poor relationship quality significantly increases the risk for CVD and mortality [26-29], underscoring the need for novel ways to maintain or restore the supportive nature of the couple with cancer. Despite the threats that cancer imposes on the health of couples and recognition that the health of intimate partners is strongly intertwined, there are no evidence-based strategies in practice that simultaneously address the physical, mental and relationship needs of this rapidly escalating demographic of the U.S. population.

**No singular program yet addresses the triple threat of declines in survivor and spouse health (physical and mental) and of their marital relationship.** In the marital literature, couple-based interventions are more effective than individual-based interventions for improving individual and couple outcomes [30-32], but these approaches focus on psychosocial and relational outcomes with no attention to physical health [33]. The physical benefits of exercise for cancer survivors are recognized [34], but the potential added benefit of bringing the spouse into an exercise program with the survivor is not. Exercise may be even more important for spouses of chronically ill partners than spouses of healthy couples yet to our knowledge there are just a few controlled trials [35] targeting caregivers, and interventions were behaviorally-focused on increasing participation in aerobic activities with only one including any measure (blood pressure) related to cardiovascular health. Prior to our work, the only exercise interventions to include the spouse and patient in an exercise intervention included a non-exercising spouse as a way to improve patient adherence to rehabilitation for osteoarthritis [36] or CVD [37].

**To fill this gap, we have developed an exercise strategy where the couple trains as a team to create a singular approach to simultaneously improve physical, mental and relationship health of the couple.** *Exercising Together* is a partnered strength training program designed to improve health and promote teamwork by the couple. Our pilot study (1R21CA137272) of *Exercising Together* performed in a group of PC couples (n=64) was highly feasible (100% retention) and improved physical fitness, mood and affectionate behavior [38-40]. We believe these outcomes occurred because we fostered skills within the couple to better collaborate, communicate, and support one another during exercise and our conceptual model theorizes this

will lead to better physical, mental and relational health within the dyad. As a next step toward broader dissemination, we need to know if a couples-based exercise approach is similarly effective for couples coping with other cancers (and when survivor gender varies), early in the illness trajectory when a couple's relationship is most vulnerable, and at reducing risk factors for chronic illness in both partners. An equally important next step is to distinguish the unique benefits of partnered training on individual and couple health from the possible benefits of exercising in a group with others and/or of engaging both partners in a new health behavior. We propose a larger, more rigorous trial of *Exercising Together*, expanding to include couples coping early on with PC, BC or CRC, clinical markers of chronic disease risk, and comparison groups that can test the unique benefits of partnered training.

Additional background for ancillary study: Rural cancer survivors are at greater risk for a variety of poor health outcomes, even many years after their cancer diagnosis, but are the least likely to have access to programs and resources to improve their health and well-being. Improving health behaviors, such as physical activity, can have a substantial impact on quality of life and survival in cancer survivors and their partners, but rural and poor adults, and particularly cancer survivors, have low rates of physical activity. Survivors living in rural areas and/or in poverty face many barriers to exercise, particularly facility-based, supervised programs which can provide a more effective, safe and supportive engaging environment than unsupervised training. There are no studies of supervised group exercise in rural and poor cancer survivors and no studies at all, even distance-based programs, that target partners and the couple as a whole. Given our successful adaptation of *Exercising Together* to remote delivery during the COVID 19 pandemic, we may be able to extend our programs to couples coping with cancer who would never be able to participate in our parent trial.

## **2.0 OBJECTIVES**

We propose a 3-group, 12-month (6 mos. of exercise training + 6-mo. follow-up) randomized trial in 294 couples comparing a supervised group program of *Exercising Together* to: 1) separate supervised group exercise (survivor-only and spouse/partner-only classes) and 2) separate unsupervised exercise where survivors and spouses/partners exercise on their own at home. We hypothesize that *Exercising Together* will significantly improve physical, mental and relationship health of couples more than separate exercise performed in a group or home setting and that benefits will persist long-term. The study addresses the following aims:

**Aim 1:** Determine the efficacy of *Exercising Together* on relationship quality (intimacy, communication and incongruence) in couples coping with PC, BC, or CRC.

**Aim 2:** Determine the efficacy of *Exercising Together* on the physical health (body composition, lipids, insulin resistance, blood pressure, inflammation, and physical function) and mental health (anxiety, depressive symptoms, fear of recurrence) of both the survivor and spouse/partner.

**Aim 3:** Determine how long individual and couple-level benefits from *Exercising Together* last.

**Aim 4 (Exploratory):** Identify the types of couples that benefit most from *Exercising Together*.

**Ancillary study:** We have received supplemental funding to conduct a pilot study with the following aim: Assess the feasibility and acceptability of remotely delivered supervised, group-based exercise to couples coping with cancer living in geographically underserved counties in Oregon. We will recruit an additional cohort of 30 couples (60 participants) coping with breast, prostate or colorectal cancer residing in five geographically underserved counties in Oregon (Wheeler, Malheur, Jefferson, Lake, and Benton counties). Data collected from the ancillary study will not be combined with data from the parent trial. Instead, data from the ancillary study will be compared to data collected in the parent trial to evaluate accrual, retention, and adherence rates, safety, intervention fidelity, and proportion of testing visits and measures completed. The ancillary

study will use separate recruitment materials, consent forms, and telephone screening scripts from the parent trial.

### **3.0 STUDY DESIGN/METHODOLOGY**

The *Exercising Together* trial is a single-blind, parallel group, randomized trial comparing 3 arms: Arm 1 (experimental): *Exercising Together* where couples perform partnered exercise in a supervised, group setting versus two comparator conditions where survivors and spouses/partners perform exercise routines separately in either a supervised group setting (Arm 2) or unsupervised at home (Arm 3). All three arms will train for a 6-month period and then be followed up 6 months later. Data will be collected at baseline, 3, 6 and 12 months.

Ancillary study: Participants who enroll in the ancillary study will not be randomized. Eligible couples who agree to participate in supervised exercise will be assigned to the *Exercising Together* program. Eligible couples who decline to participate will be offered the option to enroll in the Survivor / Spouse/Partner Home Training program.

#### **Study Arms**

All Programs: Regardless of group assignment, all participants will be expected to engage in 1-hr exercise sessions, 2 d/wk for 6 months. For participants assigned to supervised exercise training, both arms will be held at the same location within a wave and in a similar block of time to aid in enrollment, but scheduled in a way to reduce contamination (i.e., there will be 15 minutes between the end of *Exercising Together* and the beginning of Survivor-Spouse/Partner Group classes. The latter are run at the same time, but in different rooms at a single location). Class size will be limited to 9-10 couples per class (Arm 1) or 9-10 persons in a spouse/partner or survivor class (Arm 2) so that enough attention is given to participants to ensure proper form and safety. For participants assigned to home-based training they can opt to exercise at a facility or to follow an instructional DVD at home (see below).

Functional Strength Training: The basic training program for all three study arms is a functional strength training program based on recommendations for improving muscle strength in adults [41] and our prior studies in cancer survivors. Participants wear a weighted vest while performing lower body resistance exercises (chair rises, 90° squats, lunges). By wearing weighted vests, functional exercises can be performed without encountering balance-related safety risks from handheld barbells and dumbbells. Participants use free weights (dumbbells and bands) to provide overload for upper body exercises (1-arm row, bench press, push ups, triceps extension, shoulder raise). Volume of resistance exercise, determined by intensity (weight, tailored to each individual) and duration (number of repetitions and sets), is gradually increased from low weight and high repetitions to more weight and fewer repetitions over the training period for continuous overload. Unique features of our strength training program make it particularly suitable to be performed as a partnered program even among training partners who differ in their exercise capacity. We prescribe strength training as a relative intensity so that it can be tailored for each individual. Specifically, the amount of weight placed in vests for lower body exercise is prescribed as a % of body weight, so that untrained individuals with greater body mass, reflective of absolute lean mass, begin with a higher weight than smaller individuals. For upper body exercises, the individually determined amount of weight that a participant can lift the prescribed # of times, or resistance band that a participant can complete a prescribed # of repetitions correctly, will be used to set resistance. Other paired activities, such as dance, require that both partners exercise at the same absolute intensity which likely demands different levels of effort from each individual - creating safety concerns for the partner who is expending greater effort or undertraining partners who are limited by their less fit partner. The initial training progression across the study is based on our prior work and pilot study of *Exercising Together* [39, 42, 43]. Instructors, the Project

Director and [name] will confer on a monthly basis to refine individual participant efforts across arms based on tolerance and to adjust training progression.

**C.5a. *Exercising Together*:** Participants randomized to *Exercising Together* will attend supervised classes led by two certified exercise instructor(s) who are trained by the study team. One instructor will focus on instructing participants on proper form and safety during training, while the second will focus on teaching and reinforcing the teamwork (i.e., communication and supportive behaviors) within the couple during exercise. Both partners will be expected to attend the same exercise sessions, but partners can attend separately in the event the other cannot, though we will discourage this except for unusual circumstances (i.e., illness). Participants attend classes along with other couples from the same recruitment wave to insure that progression of exercise is consistent among participants.

Unlike group exercise where individuals perform the same exercise in synchronized fashion led by an exercise instructor, partnered strength training requires training partners to interact with one another, verbally and physically during training. In *Exercising Together*, the survivor and his/her spouse/partner will build skills to work as a team. We will foster the skills a couple uses as they collaborate toward a common goal (e.g., improve their health and functioning). Based on our conceptual model we incorporate skills that promote and reinforce what we feel are the key characteristics of a successful team (communication, motivation, and support) and use this to guide training of couples to maximize their teamwork during each exercise session. During each exercise, one partner will assume the role of “trainer” and the other “exerciser” and then switch. We hypothesize that the teamwork skills used when training will permeate outside of the exercise setting and enhance the overall relationship of the couple. The exercise instructor focusing on teamwork will discuss the role of training partners in the early phase of the intervention and will continually work with participants to develop their roles as training partners and functioning as a team using the principles of collaboration, communication and supportive behaviors. In addition to partner roles, we will build teamwork and couple interactions by having participants perform 2-4 tandem exercises per session (i.e., lunge with ball pass, standing tandem balance). A tandem exercise is one where the couple must work together to complete the exercise. Tandem exercises require the couple to communicate and interact both non-verbally and verbally and provide a challenging but fun opportunity for direct interaction around exercise. We can modify tandem exercises if one partner is more limited than the other, yet retain the interactive element.

**Survivor / Spouse/Partner Group Training:** Participants will attend separate group exercise classes for survivors and for spouses/partners and a certified exercise instructor will lead each class. The way that we structure the time and location of supervised classes will allow for the two trainers leading *Exercising Together* classes to then each lead a survivor or spouse/partner group class. Survivor and spouse/partner classes will be run at the same time at the same location to make it easier for spouses/partners who need to travel together; however, they are not required to do so. Each group will follow the general functional strength training program similar to our prior studies with BC or PC survivors only [42, 43], without any element of teamwork.

Participants assigned to supervised exercise may perform all exercise sessions remotely (e.g., at home) using videoconferencing software. The necessary exercise equipment and a webcam may be provided if needed, and will be returned at the end of study. Participants will receive written and verbal instructions for installing and using videoconferencing software. During these web-based, group video conferences, the exercise instructors will observe and instruct participants using the same format as on-site classes.

**Ancillary study:** Participants enrolled in the ancillary study and assigned to *Exercising Together* will perform exercise sessions remotely as described above.

Participation in the ancillary study requires the ability to video conference with the research team. As needed, couples may be provided an Internet capable device with sufficient screen size to view the participant in a standing position (i.e., Chromebook or tablet). Devices will be collected when participation is complete.

**Survivor / Spouse/Partner Home Training:** Participants will be given equipment (vest, weights and/or resistance bands) and a program to do at home or a facility, depending on their preference. Within two weeks of randomization, each couple will have two one-hour training sessions with an exercise trainer who will teach them our functional strength training program, modified to their abilities and for home or facility use. We will also provide them with a general DVD of the strength program to follow at home. The trainer will check in weekly by phone in month 1 and monthly thereafter to assess tolerance and modify programs as needed. We have delivered home-based resistance training this way in our prior studies without any related injuries [42-44]. Participants can perform the program on days (allowing for 48 hours between sessions) and at times convenient for them. There is no requirement that partners exercise at the same time, though we will track the degree to which couples may do so in case we need to account for this in analyses.

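### Remote delivery leaves Arm 2 without a stated rule for keeping partners physically apart, and co-exercise there is not tracked by session, so the Arm 1 v Arm 2 contrast may be diluted without the trial being able to say by how much

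*Combined protocol and SAP*

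**What the plan says.** Section 1.0 gives the purpose of the comparators: to separate the benefit of training as a pair from the benefit of exercising in a group, or of both partners taking up a new behaviour.

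Section 3.0, Study Arms, defines Arm 2 by three features:

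- **Separate classes and instructors:** "Participants will attend separate group exercise classes for survivors and for spouses/partners and a certified exercise instructor will lead each class".
- **Content:** the program is delivered "without any element of teamwork".
- **Place:** in the All Programs paragraph, of the survivor and partner classes, "The latter are run at the same time, but in different rooms at a single location". The supervised arms are also "scheduled in a way to reduce contamination", with a 15-minute gap between Arm 1 and Arm 2 classes.

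The Arm 2 paragraph adds "Survivor and spouse/partner classes will be run at the same time at the same location" and gives shared travel as the reason.

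The next paragraph opens both supervised arms to home delivery: "Participants assigned to supervised exercise may perform all exercise sessions remotely (e.g., at home) using videoconferencing software". Instructors are to watch and teach in the on-site format. Rooms, devices and timing within the home are not mentioned.

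For Arm 3 the Home Training paragraph says: "There is no requirement that partners exercise at the same time, though we will track the degree to which couples may do so". It adds that this is in case the analysis needs to allow for it. No matching sentence exists for Arm 2.

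**The concern.** Arm 3 differs from Arm 1 on supervision, on group setting and on partnering, and it permits joint exercise. Arm 2 matches Arm 1 on supervision and group setting. The Arm 1 v Arm 2 contrast therefore carries the claim that partnering itself matters.

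The one rule that keeps Arm 2 partners in different physical spaces is written for a facility. At home, a co-residing couple following the plan as written could do their two classes in the same room. If some of the relational benefit comes simply from exercising next to one's partner, Arm 2 would pick up part of it and the contrast would shrink. Without session-level information, a small or null Arm 1 v Arm 2 difference would be harder to read: partnering might add little, or the comparator might have been partly partnered.

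**Working it through.** **1. Setting the provisions side by side**

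| Feature separating Arm 2 partners | On site | Remote |
|---|---|---|
| Separate survivor and partner classes | Stated | Appears to carry over (same teaching format) |
| An instructor for each class | Stated | Appears to carry over |
| No teamwork content | Stated | Appears to carry over |
| Different rooms | Stated | Nothing stated |
| Classes at the same time | Stated, with a travel rationale | Not stated; could be inferred from the common format |

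Section 5.0 requires survivors to live with the participating partner. The remote precautions in Section 10.0 (Protection Against Risk) concern safety only.

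**2. What is recorded on co-exercise**

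- *Arm 3:* tracking for possible use in analysis (Home Training). The method is not specified.
- *All arms:* a 0–4 rating of exercising together, with an open-ended follow-up on types of activity (Descriptive Measures), scheduled at baseline, 3, 6 and 12 months (Section 8.0, Schedule of Events). It does not distinguish study sessions from other joint exercise. The stated analytic use of shared-activity data is Aim 3 (Six-Month Follow-Up Period).
- *Attendance logs:* the instructor records sessions completed (Process Measures). Delivery mode and the partner's presence are not mentioned.
- *Aim 1 model (Section 13.0):* two group dummies. The covariates to be considered are age, comorbidities and time since diagnosis. There is no term for delivery mode or co-exercise.

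**3. The plan's own figures**

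Inflation for 10% attrition: 264 / (1 − 0.10) = 293.3, rounded up to 294. This reproduces.

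The stated power of 0.80 at d=0.40 with 264 couples cannot be reproduced, because alpha and the variance components are not given. The protocol attaches it to change over time, not to a named pair of arms. A simple two-group check with 264 / 3 = 88 couples per arm, two-sided alpha 0.05, gives 0.756. That is not the protocol's formula and does not show 0.80 to be wrong.

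**4. Illustration of dilution**

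Assumptions, none of them from the documents: d=0.40 and power 0.80 refer to Arm 1 v Arm 2, and alpha is 0.05 two-sided. Let k = (share of Arm 2 couples training side by side) × (fraction of the partnering effect they then obtain).

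- Remaining effect = 0.40 × (1 − k)
- Power = Φ[2.80 × (1 − k) − 1.96], where 2.80 = 1.96 + 0.84
- Couples to randomize to restore 0.80 = 264 / (1 − k)² / 0.9, rounded up

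| k | One way to reach it | d | Power | Couples randomized |
|---|---|---|---|---|
| 0 | no co-exercise, or no carry-over | 0.40 | 0.80 | 294 |
| 0.0625 | 25% × one quarter | 0.375 | 0.75 | 334 |
| 0.125 | 25% × one half | 0.35 | 0.69 | 384 |
| 0.25 | 50% × one half | 0.30 | 0.56 | 522 |
| 0.50 | 100% × one half | 0.20 | 0.29 | 1,174 |

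The documents give neither the remote share nor any carry-over, so no row can be called likely.

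**The case against.** The strongest reply is that side-by-side exercise is not the Arm 1 intervention. Arm 1 uses alternating trainer and exerciser roles, 2–4 tandem exercises per session and a second instructor devoted to teamwork. An Arm 2 couple in one room, each following their own class, gets none of these by design. This stands, and it limits the harm to dilution. A reader might infer that remote delivery abolishes the separation that defines Arm 2. The documents do not support that, because three of its features appear to carry over.

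A reader might also take it that remote classes definitely run at the same time. The protocol states concurrency only for a shared location, for a travel reason that does not apply at home. Two concurrent classes with two instructors would also in practice need two video connections, which makes one shared screen less likely. This stands: simultaneous home classes are possible, not established.

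Nor is it right that nothing would show joint exercise. The 0–4 rating is taken at 3 and 6 months in every arm, instructors watch remote participants, and the Post-Intervention Survey asks about experience of the assigned program. The Arm 3 wording does not promise session-level records either. What remains is that none of these sources is set up to identify co-exercise during Arm 2 sessions, and none is tied to the Arm 1 v Arm 2 analysis.

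Finally, the lower rows of the power table should not be read as an estimate. The upper case needs every Arm 2 couple to be remote and co-exercising, and the half carry-over has no source.

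**Conclusion.** The concern holds as a gap in specification and tracking. The plan permits all-remote delivery for co-residing Arm 2 couples, states no substitute for the different-rooms rule, and states co-exercise tracking for analysis only in Arm 3. Following it as written could dilute the contrast that best isolates partnering.

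The size is unknown. It is zero if remote couples train apart or if side-by-side exercise carries no relational benefit, and the power figures are illustrative only. If co-exercise does help, the bias runs toward no difference: a clear Arm 1 advantage would stand and, if anything, be understated, while a null result would be harder to interpret. To say that a null result would be uninterpretable goes further than the documents allow.

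**What to change.** 1. In the remote-delivery text, instruct Arm 2 survivors and partners to join their own class separately: in a separate space where feasible, or with the two video classes offset in time. State whether remote classes are concurrent. Mandatory separate rooms or a loaned device for every couple is not needed.
2. Add to the instructor's attendance log, per session, the delivery mode and whether the partner was exercising alongside.
3. Extend the Arm 3 co-exercise tracking to Arm 2, in the same form.
4. Pre-specify a sensitivity report of Arm 1 v Arm 2 by delivery mode and by co-exercise, also using the 0–4 shared-exercise rating at 3 and 6 months. Keep the intention-to-treat contrast as the main result. Co-exercise arises after randomization, so that split is descriptive. The same applies to delivery mode if couples choose it after assignment, so record how and when it was decided.

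Cost: participant instructions, a small logging burden and, for some couples, an offset class time or a second device. The device-loan text currently sits under the ancillary study; for the supervised arms the protocol mentions exercise equipment and a webcam. If training has already finished, reporting by delivery mode and by the 3- and 6-month rating is still possible where records allow.
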